5.3 Study Design and Plan

Patients recruited from the endoscopy unit will have been referred by their responsible clinician to undergo a lower gastrointestinal endoscopy (which involves a telescope test to visualise the colon). Others may be attending for colonoscopy as part of the bowel cancer screening programme or as part of routine surveillance. When patients attend the endoscopy unit, a member of the research team will discuss the research project with the patient, explain that the study involves sampling of their breath and urine while they are waiting for their endoscopy. Patients may also be asked to consent to the use of the colonic air collected during colonoscopy for analysis. Patients will then be provided with a patient

information leaflet, (see Participant Information Leaflet version 3.0 24/04/2017). Should the patient agree to participate they will be asked to sign a written consent form (see Consent Form Version 2.0 15/02/2017).

Patients recruited from secondary care will be approached either before or after a routine appointment that they will be attending as part of their clinical care. This could include general colorectal clinics, pre-operative colorectal clinics, oncology clinics, theatres or on hospital wards.

The project will be explained to them and they will be provided with an information leaflet. If they agree to participate they will be asked to sign a written consent form in order to provide breath and urine samples for the research project. Consent for colonic air sampling is not applicable to the majority of secondary care patients, only to those having a colonoscopy. No additional invasive procedures will be undertaken for the purposes of this study. A subset of patients with known cancer who are due to have a cancer resection may be asked to provide additional breath and urine samples 6–8 weeks following surgical resection of their tumour and/or if their disease should recur.

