Patients attending for colonoscopy will be fasted for a minimum of six hours prior to their breath sample collection. This is normal routine practice for patients undergoing endoscopy and therefore will not alter their treatment pathway. All breath samples will be retrieved prior to endoscopy. In other secondary care settings patients will not be specifically asked to fast prior to giving breath or urine samples but note will be made of how long they have fasted for. Patients will be asked to give a number of exhalations into a breath sampling device until a defined volume of breath has been sampled. This involves performing normal tidal breathing whilst wearing a face mask, and takes around 2 minutes on average. Patients will also be asked to perform a single deep nasal inhalation followed by complete exhalation via their mouth into a secure GastroCHECK steel breath bag (500 mL) via a 1 mL Luer-Lok syringe (Terumo Europe, Leuven, Belgium). Patients at St Mary's Hospital will also be asked to breathe directly into a mass spectrometer machine. The mass spectrometer is a self-contained mobile device which can be easily moved between clinical areas within St Mary's Hospital. Sampling by this method will involve a single deep nasal inhalation followed by complete exhalation via their mouth into a plastic cylinder connected to a tube leading to the mass spectrometer itself. We expect the breath sampling process to take no longer than 5–10 minutes in total. Patients will be requested to pass urine into a standardised 60ml urine specimen vial, which will be immediately sealed. 20ml of urine will be aliquoted into a standard 60ml specimen vial.

Of patients attending for colonoscopy, a subset will be asked to consent to have air from their colon collected. This air comes up from the colon through the colonoscope suction channels. Suctioning of air is a routine part of the examination, but for this study we will be collecting it for analysis. Collection is done via a small suction pump connected to a fine bore tube that is passed through the suction channel of the colonoscope. Sampling in this way will add no more than a few minutes (<4 minutes) on to the procedure time.

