6.2 Recruitment and Informed Consent Procedures

A member of the research team will identify and approach patients when they attend for a lower gastrointestinal endoscopy. All patients attending for colonoscopy within the specified age range are potentially eligible for this study. If the patient is in agreement, a member of the research team will explain the research project and provide a written information leaflet (see Participant Information Leaflet version 3.0 24/04/2017). Patients will be given adequate time to decide if they wish to participate and should they agree they will complete a written consent form (see Consent Form Version 2.0 15/02/2017).

A member of the research team will identify patients when they attend for a clinic appointment by discussion with the Consultant clinician responsible for the clinic. A member of the research team will approach patients when they attend for their clinic or pre-assessment appointment prior to planned surgery. Patients will have the research project explained to them and will be provided with a written information leaflet (see Participant Information Leaflet version 3.0 24/04/2017). Patients will be provided with adequate time to decide if they wish to participate and should they agree they would complete a written consent form (see Consent Form Version 2.0 15/02/2017).

All of the above would occur at one of the patient's routine clinical attendances and would not require any additional patient attendances.

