7. STATISTICAL CONSIDERATIONS

Both univariate and multivariate data analysis techniques will be applied to the results to 1) identify VOC components with the best discriminating ability between the groups and 2) to develop a multivariate discriminant analysis model.

Mann-Whitney U test will be used to compare the measured metabolite concentrations between the study groups. A p value <0.05 will be taken as the level to indicate statistical significance.

Non-parametric (Kruskal-Wallis) ANOVA test will be used to compare the measured metabolite levels between the study groups. Statistically significant metabolites will be selected using False Discovery Rate (FDR) adjusted p value threshold such that less than 5% of discovered candidate markers are false positives (i.e. q-value <0.05).

The FDR strategy will be based on Benjamini-Hochberg procedure.

Receiver operating characteristic (ROC) curves will be used to determine the accuracy of a diagnostic test in classifying those with and without colorectal disease. The metabolite concentrations that exhibit significant differences ($q < 0.05$) between the cancer and positive controls (including adenomatous polyps) will be included as variables for the proposed diagnostic test. The linear discriminant analysis based on multivariate logistic regression will be subsequently used to derive a combination of the metabolite concentrations for sample classification. The optimum threshold for group discrimination will be calculated to achieve the highest possible classification accuracy. The predictive capacity of the model will be assessed on independent sample set, as described below.

Validation

The Breath and Urine metabolite model for the prediction of colorectal disease developed in the previous studies will be used to assign risk of disease in a prospective cohort. Investigators undertaking metabolite sampling and analysis will be blinded to the results of the endoscopy. Comparison of predicted disease risk and actual endoscopy findings will then be made, and the overall diagnostic accuracy (sensitivity, specificity, positive and negative predictive value, ROC curve analysis) for this non-invasive diagnostic investigation will be determined. Colonic air VOC profiles will be used for validation of paired breath results, and to gain further understanding of the mechanism of VOC production in humans.

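### Section 7 claims blinding for every sample, but it cannot be assured at sampling for patients recruited with a known diagnosis, and nothing keeps them out of the validation estimate

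*Combined protocol and SAP*

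**What the plan says.** The Validation part of Section 7 sets the blind in one sentence: "Investigators undertaking metabolite sampling and analysis will be blinded to the results of the endoscopy". It covers both sampling and analysis and makes no distinction by recruitment route or sample type. The accuracy measures follow from the next step: "Comparison of predicted disease risk and actual endoscopy findings will then be made".

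Recruitment has two routes. In the endoscopy unit, Section 5.3 has breath and urine sampled while the patient waits, and breath always before the procedure. Outside it, Section 5.3 lists "general colorectal clinics, pre-operative colorectal clinics, oncology clinics, theatres or on hospital wards". Section 6.2 has the research team "identify patients when they attend for a clinic appointment by discussion with the Consultant clinician responsible for the clinic", and approach patients at clinic or pre-assessment ahead of planned surgery. Section 5.3 also refers to "A subset of patients with known cancer who are due to have a cancer resection", who may be sampled again after resection or at recurrence.

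Two sampling methods need separate mention. On direct breath, Section 5.3 says: "Patients at St Mary's Hospital will also be asked to breathe directly into a mass spectrometer machine". On colonic air it says: "Collection is done via a small suction pump connected to a fine bore tube that is passed through the suction channel of the colonoscope".

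Section 11 gives specimens a study number, linked to a database under the Chief Investigator's control.

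**The concern.** Diagnostic accuracy is the primary aim (Section 4.1), and this sentence is the plan's only stated protection against the index test being read in the light of the diagnosis. It describes a blind that timing delivers in one recruitment route but not in the other.

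If patients with established cancer supply part of the case group, their samples can be taken by someone who knows they are cases, while controls sampled before endoscopy are taken by someone who does not know the outcome. Handling that depends on knowledge of case status would tend to make the test look better than it is. Section 7 gives no fixed rule for accepting, repeating or excluding a sample that would guard against this. A report that called the whole validation blinded would then claim more than the design provides.

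**Working it through.** The plan states no figure on this point and none can be derived, so the check is a trace. For each stream and sample type, does the diagnosis exist and can it be seen, first at sampling and then at measurement?

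| Stream and sample | At sampling | At measurement |
|---|---|---|
| Endoscopy unit: breath and urine | Blind by timing; that endoscopy has not happened (5.3) | Can be blind through the study number (11) |
| Endoscopy unit: direct breath, St Mary's | Blind by timing | Same act as sampling, so also blind by timing |
| Known diagnosis: tubes, bags, urine | Sampler can know the diagnosis (5.3, 6.2) | Tubes and urine can be blind if coded; no coding step specific to bags is described |
| Known diagnosis: direct breath, St Mary's | Operator can know the diagnosis | Same act, so the operator can be unblinded here too |
| Colonic air | Collected during the colonoscopy; collector may see the findings | Tube goes capped to the laboratory, so can be blind |

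1. *Does the known-diagnosis stream reach the accuracy estimate?* The eligibility criteria (5.1, 5.2) admit patients seen in other hospital settings and do not exclude an established cancer. Secondary aim (ii) in Section 4.1 concerns a new group of patients who have colorectal cancer and does not require that they be undiagnosed at sampling. Section 7 speaks of a prospective cohort without defining its members. Nothing says these patients enter, and nothing keeps them out. If they enter, the sampling blind cannot be assured for them. If they do not, the plan should say so.

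2. *Is the laboratory blind secured?* Section 5.3 allows up to 48 hours before tubes are analysed, and Section 11 stores urine, so an endoscopy result can exist before analysis even in the pre-endoscopy stream. The analyst's blind then depends on coding and access. The study number hides identity, but no text withholds recruitment setting or diagnosis from analysts, says who may open the database link, or records the predicted risk before linkage. The blind is achievable; the means are not written down.

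3. *Does colonic air affect the result?* Section 4.1 makes breath and urine the index test. Colonic air is a subset comparison, used in Section 7 to support paired breath results and to study mechanism. The paired breath has already been taken. Unblinded collection of colonic air therefore does not unblind the breath or urine result.

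**The case against.** The strongest defence is that the sentence concerns the endoscopy result, that the validation compares predictions with endoscopy findings, and that breath in that route is always taken first. On this reading the validation cohort is the endoscopy cohort and the blind holds. The defence is right for that cohort. It does not settle the matter, because the cohort is not defined and the other route is open to the same study.

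Several stronger conclusions might be inferred, and the documents do not support them:

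- *That the accuracy result as a whole is unblinded.* Pre-endoscopy samples are blind at sampling, and coded tubes and urine can be analysed blind in either stream.
- *That direct breath at St Mary's breaks the blind in itself.* Before endoscopy there is no result to see. It adds a problem only where the diagnosis is already known.
- *That every clinic patient is a known case.* The settings include general colorectal clinics, and symptomatic patients are eligible. Discussion with a consultant means the sampler can know, not that the sampler always does. The sentence on known cancer concerns additional samples, which relate largely to the recurrence aim.
- *That the bias can be sized.* Starting from the pilot sensitivity of 85%, if a fraction f of false-negative samples were discarded, apparent sensitivity would be 0.85/(0.85 + 0.15(1 − f)). With f = 10%, 20% or 50% this gives 86.3%, 87.6% or 91.9%. The arithmetic is sound, but the values of f are assumptions. Discarding false negatives selectively also requires knowledge of the model output, which someone capping a tube does not have. This shows a direction under a particular mechanism and is not an estimate.

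The missing lock on predicted risk is also an omission of detail, not a contradiction: Section 7 already puts risk assignment before comparison.

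**Conclusion.** The point holds for one stream. Section 7 promises a blind at sampling that cannot be assured for patients whose diagnosis is established when they are recruited. For direct breath at St Mary's, the same operator can be unblinded at measurement. No section keeps these patients out of the validation estimate. For breath and urine taken before endoscopy the statement can stand, provided the laboratory blind is specified.

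The size of any bias cannot be computed. It would depend on the share of known cancers in the case group and on how samples are accepted or rejected, and the documents give neither. The conclusion assumes only that staff recruiting in pre-operative and oncology settings can learn the diagnosis there, which the described route of identification makes likely. Surveillance patients may also have earlier diagnoses known to the team, but those are not the endoscopy result to which the blinding sentence refers.

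**What to change.** Amend Section 7 as follows.

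1. Limit the blinding statement to samples taken before endoscopy from patients without an established diagnosis, and name that cohort as the blinded validation estimate. Define what counts as established.
2. Report patients with a known diagnosis separately, including their direct breath readings, and do not describe those results as blinded validation.
3. Give laboratory staff tubes, bags and urine under a code that carries neither recruitment setting nor diagnosis. Apply fixed sample acceptance and exclusion rules under that code, and state who holds the link.
4. Lock and date each patient's predicted risk before it is linked to the endoscopy finding.
5. State that colonic air is not blinded at collection.

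This takes protocol and procedure wording, a change to sample coding and a dated record of predictions. It needs no extra patients or procedures. The downside is that the blinded estimate rests on fewer cancers and is less precise; how many fewer cannot be stated, because the share of known cancers is not given.

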3. INTRODUCTION

3.1 Background

Colorectal cancer (CRC) is the 2nd commonest cause of cancer death in the UK. Survival rates are among the lowest in Europe (1) and 26% of patients present as an emergency, frequently having visited their GP before diagnosis (2-4). If diagnosed early, CRC survival rates exceed 90% (5). Whilst, reducing delay in diagnosis is therefore considered key to improving outcomes [6], initiatives to reduce delay have thus far been largely unsuccessful (6, 7). In order to improve the diagnosis of CRC, efforts should be made to determine how the risk of CRC can be assessed using sensitive primary care tests that are: valid; easy to perform, and; well tolerated by patients.

CRC screening programmes rely on detection of early-stage cancer using the faecal occult blood test (FOBT) with colonoscopy in those patients with a positive test. Trials have shown that this screening method reduced CRC mortality but not incidence rates. Even if UK CRC incidence rates remain constant, as they have for the past 30 years, with an aging population the number of cases and treatment cost are set to double in the next 50 years. The Bowel Scope programme is also being rolled out across the UK currently, aiming to perform flexible sigmoidoscopy on every person at the age of 55. Invasive screening reduces mortality but is not without risk to patients and pressurises an already overburdened healthcare service.

Risk of CRC in symptomatic patients can be assessed by different methods:

- (I) *Flexible sigmoidoscopy and colonoscopy*: The NHS currently has insufficient trained endoscopists to perform the number of procedures that would be required if flexible sigmoidoscopy were used as a first-line test for symptoms with predictive values below 3%.
- (II) *Guaiac FOBT* has good sensitivity (87-98% in CRC detection), but highly variable and often unsatisfactory specificity (13-79%), requiring the repetition of the test on multiple stool samples. To date, the FOBT is neither recommended nor available for use as an intermediate test (8-11).

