3.2 Rationale

Colonoscopy remains the gold-standard investigation for the assessment of patients with lower gastrointestinal symptoms and considered at risk of colorectal cancer. Colonoscopy is an expensive investigation that is uncomfortable for the patient and not without important risks including visceral perforation and bleeding.

A breath test is a non-invasive investigation. The use of a breath test as a triage investigation in symptomatic patients could identify high-risk patients who should be referred for colonoscopy at an earlier stage, increase the proportion of appropriate referrals from primary care, and improve NICE guidelines which may currently miss particularly younger patients (43). If a GP is presented with a patient with gastrointestinal symptoms that do not prompt referral under NICE guidelines, he/she would not need to watch-and-wait to see if symptoms worsen but could offer the test immediately. The GP would order a breath test in much the same way as routine blood tests, with a single breath collection assessing for individual or multiple cancers. A nurse can perform the test and send breath samples to a regional laboratory for analysis. A positive result would warrant immediate referral. A negative test would permit the GP to reassure the patient and offer retesting if symptoms persist. Furthermore if we could develop a breath test that can discriminate colonic adenomas, the test would have further a potential application within the screening programme.

A breath test could also be used to detect recurrence in patients post-resection for their colorectal cancer, allowing earlier detection and limiting invasive testing in those who are free of recurrence.

Previous pilot study data for colorectal cancer detection by our group produced a diagnostic model with a sensitivity of 85% and specificity of 84% for colorectal cancer. The next stage of this research and the subject of this current proposal is to assess the influence of lower gastrointestinal diseases on VOC exhaled breath and urine. The external validation of this VOC breath model in a large multi-centre study will provide this risk-stratification tool for future clinical practice.

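### PPV and NPV are planned from a cohort with no defined make-up or stated prevalence, so they would hold only for that recruitment mix and not for the GP triage use the protocol describes

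*Combined protocol and SAP*

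**What the plan says.** The Validation part of section 7 says that the existing model "will be used to assign risk of disease in a prospective cohort". It continues: "Comparison of predicted disease risk and actual endoscopy findings will then be made". The measures to be reported are sensitivity, specificity, "positive and negative predictive value" and ROC analysis. The cohort is not described further: there is no restriction by recruitment route or prior diagnosis, no expected prevalence, and no plan to recalculate predictive values for another setting.

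Section 5.3 describes two recruitment routes. The endoscopy route takes referred patients, and "Others may be attending for colonoscopy as part of the bowel cancer screening programme or as part of routine surveillance". The other secondary-care route is open-ended: "This could include general colorectal clinics, pre-operative colorectal clinics, oncology clinics, theatres or on hospital wards". The same section provides for extra samples from some patients with known cancer awaiting resection. Section 5.2 excludes only on capacity or consent and on age, so a prior cancer diagnosis is no bar. Section 6.2 adds that patients may be approached at pre-assessment before planned surgery. No route has a quota or an expected share of the 2000.

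Section 3.2 describes the intended use as triage of symptomatic patients by a GP, including patients who do not meet referral criteria. A positive result leads to referral. For the other result, "A negative test would permit the GP to reassure the patient and offer retesting if symptoms persist".

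**The concern.** Sensitivity and specificity are conditional on disease status, so the proportion of cancers in the sample does not by itself change them. PPV and NPV do depend directly on that proportion. Here the proportion follows from how many patients are approached in each setting, which the protocol leaves open. Two recruitment teams using the same test could report very different PPVs.

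Referring on a positive result and reassuring on a negative one are PPV and NPV decisions. No participant is recruited in primary care, where section 3.2 places those decisions. Diagnostic accuracy is the primary aim (section 4.1), so these values would be headline results. A PPV taken from a mix richer in cancer than the GP's patients would make the test look more decisive than it would be there.

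**Working it through.** **No plan figure to reproduce.** The protocol states no PPV, NPV, cohort prevalence or precision target. The check is therefore how far the predictive values move when only prevalence changes.

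**Inputs**
- Sensitivity (Se) 0.85 and specificity (Sp) 0.84 for colorectal cancer: pilot model, sections 3.1 and 3.2.
- N = 2000: section 2.
- Triage prevalence: not given. Section 3.1 mentions "symptoms with predictive values below 3" per cent when discussing endoscopist capacity. It is used here only as a proxy, with 1% to 3% as the assumed range.
- Endoscopy-only prevalence: not given; 5% assumed.
- Mixed cohort: not given. Assumed 4% in patients without a prior diagnosis, plus k = 50, 100 or 200 known cancers among the 2000.

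**Formulas**
- PPV = Se·p / [Se·p + (1 − Sp)(1 − p)]
- NPV = Sp(1 − p) / [Sp(1 − p) + (1 − Se)p]
- Mixed cohort: p = [0.04(2000 − k) + k] / 2000

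**Mixed-cohort prevalence**
- k = 50: (78 + 50)/2000 = 6.4%
- k = 100: (76 + 100)/2000 = 8.8%
- k = 200: (72 + 200)/2000 = 13.6%

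**Worked case at 3%**
- PPV = 0.0255 / (0.0255 + 0.1552) = 14.1%
- NPV = 0.8148 / (0.8148 + 0.0045) = 99.5%

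| Setting (all prevalences assumed) | p | PPV | NPV |
|---|---|---|---|
| Triage, low | 1% | 5.1% | 99.8% |
| Triage, proxy | 3% | 14.1% | 99.5% |
| Endoscopy only | 5% | 21.9% | 99.1% |
| Mixed, k = 50 | 6.4% | 26.6% | 98.8% |
| Mixed, k = 100 | 8.8% | 33.9% | 98.3% |
| Mixed, k = 200 | 13.6% | 45.5% | 97.3% |

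**Size.** Against the 3% value, the mixed-cohort PPVs are larger by factors of 26.6/14.1 = 1.9, 33.9/14.1 = 2.4 and 45.5/14.1 = 3.2. The endoscopy-only PPV is larger by 21.9/14.1 = 1.6. NPV moves the other way, by 99.5 − 97.3 = 2.2 percentage points at most. The test itself is identical in every row.

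**The case against.** A reader might infer that section 7 pools all 2000 patients, and that pre-operative and oncology clinics set the cancer prevalence. The documents support neither. Section 7 speaks only of a prospective cohort. Its endoscopy reference standard and its blinding to endoscopy results both fit a validation set drawn from endoscopy patients, whose breath samples section 5.3 says are taken beforehand. Patients with known cancer also have other possible uses under section 4.1, such as model refinement and the study of recurrence. The clinics are some of several settings, and no shares are given. The counts of 50 to 200 known cancers are illustrations, not plan figures.

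It can also be said that observed PPV and NPV are correct for the cohort in which they are observed, and that section 3.2 describes a future use without promising a primary-care PPV. The 3% figure is not offered as a triage prevalence. Section 7 also refers to prediction of colorectal disease, and if that includes adenomas the cancer figures above do not describe the planned PPV. Finally, the NPV error understates how reassuring a negative result is, so it does not favour the test.

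All of this limits the size and certainty of the point without removing it. An endoscopy-only cohort is still not a GP cohort: it contains patients already referred, under surveillance or invited through screening, and nothing ties its prevalence to that of triage. The unclear target condition is a further reason why a reported PPV could not be interpreted.

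**Conclusion.** The point holds in a limited form. As written, section 7 would give PPV and NPV valid only for a recruitment mix that the protocol does not specify. They would not carry over to GP triage, whether or not patients with known cancer are included. PPV would be too high and NPV conservatively low whenever cohort prevalence exceeds triage prevalence. That is plausible for a secondary-care cohort that may include known cancers, but the documents give no figure that establishes it.

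In the assumed scenarios PPV is inflated about 1.6-fold (endoscopy only) to 3.2-fold against a 3% comparator, and by more against a lower one. These figures rest on cancer as the target, the pilot's sensitivity and specificity, and assumed prevalences throughout.

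Prevalence weighting alone leaves sensitivity, specificity and the ROC curve intact. They could be affected by a separate problem. Patients with established cancer may differ from those yet to be diagnosed, and section 5.3 has colonoscopy patients fast while clinic patients need not. Recalculating PPV and NPV would not remove such bias, so the choice of patients for estimating sensitivity and specificity also matters.

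**What to change.** Amend the Validation part of section 7, before the data are analysed, to:

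1. State the target condition to which PPV and NPV refer (cancer, or a defined wider group).
2. Estimate sensitivity and specificity in patients without a prior diagnosis who were sampled before endoscopy, and show results for other recruitment routes separately.
3. Derive PPV and NPV by Bayes' rule at stated intended-use prevalences, for example 1%, 3% and 5%, with the uncertainty in sensitivity and specificity carried through to intervals.
4. Report any crude PPV or NPV only beside the observed prevalence of the cohort it came from.

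The cost is a short amendment and a few lines of analysis, with no new patients or samples. The reported PPV will look less favourable. The undiagnosed subset will also hold fewer cancers. In the assumed k = 200 case it has 0.04 × 1800 = 72 instead of 272, so the 95% half-width for a sensitivity of 85% grows from 1.96√(0.85 × 0.15/272) = 4.2 to 1.96√(0.85 × 0.15/72) = 8.2 percentage points. The projection still assumes that sensitivity and specificity carry over from secondary to primary care, and the report should say so.
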